## 5. Study Objectives or Hypotheses

The aim of this study is to evaluate the efficacy, safety, and tolerability of PRX-00023 following 12 weeks of treatment in patients with localization-related epilepsy.

### 5.1 Primary Hypothesis:

PRX-00023 treatment will lead to reduced seizure frequency compared with placebo.

### 5.2 Secondary Hypotheses

1. PRX-00023 will lead to improved anxiety and depression rating scores compared with placebo.
2. The degree of baseline 5HT1A receptor binding reduction in the epileptic focus will predict drug response.
3. Polymorphisms in SERT, TPNH, COMT, BDNF and GABA genes that have been associated with psychiatric disorders and epileptogenesis may be related to drug response.

### 5.3 Safety Hypothesis

PRX-00023 is safe and well tolerated in adult patients with localization-related epilepsy.

## 6. Subjects

### 6.1 Description of Study Population

The study will accrue up to thirty patients aged 18 to 65 inclusive with localization-related epilepsy with the goal of obtaining 20 completers, unless a carry-over effect is detected, in which case 24 completers would be required (see statistical analysis section 11. 4 and 11.41).

### 6.2 Inclusion criteria

1. Enrolled in protocol 01-N-0139
2. Age 18 – 65 years
3. Localization-related epilepsy diagnosed by standard clinical criteria that has not responded to treatment with up to two standard antiepileptic drugs either sequentially or in combination.
4. Patients must be able to provide informed consent.
5. Patients must be able to remain on their baseline AED drugs and doses for the duration of the study.
6. Patients must be able to use seizure calendars to record seizures throughout the trial.
7. Experience 4 seizures within a 6-week period.

### 6.3 Exclusion Criteria

1. Pregnancy or lactation
2. Women of child-bearing potential and men who are unable or unwilling to take adequate contraceptive precautions, including one of the following:  
hormonal contraception (birth control pills, injected hormones or vaginal ring); intrauterine device; barrier methods (condom or diaphragm) combined with spermicide; surgical sterilization (hysterectomy, tubal ligation, or vasectomy in a partner).
2. Current treatment for another significant medical disorder, such as diabetes, or heart disease, or an untreated disorder, that is discovered during the screening examination and might interfere with the study and is determined by the PI to warrant exclusion of the participant.
3. An abnormality on clinical laboratory tests, physical examination, EEG or ECG that might increase the risk associated with trial participation or investigational product administration, such as hepatic enzyme elevation greater than twice normal, or hematocrit lower than 30.
4. A level 4 or 5 on the Columbia Suicide Severity Rating Scale rating for symptoms during the last month
5. Concomitant treatment with more than 2 AEDs.
6. Evidence for a potentially progressive neurologic disorder, such as an astrocytoma
7. Use of sublingual lorazepam for seizure clusters more than once per week.
8. Use of any of the following with less than required interval

Prohibited Medications/Classes	Required interval Period (Weeks Prior to baseline)
Any other Investigational drugs	4
benzodiazepines	Chronic or daily use: 4 Occasional or PRN use: 1
MAO Inhibitors anti depressant	4
Citalopram	4
Buspirone	2
other psychotropic medicines	2
potent CYP3A4 inducers/inhibitors:	2

 
• itraconazole
 
• ketoconazole
 
• HIV antivirals
 
• clarithromycin
 
• phenytoin
 
• barbiturates
 
• rifampin
 
• St. John's Wort
 
	
propranolol	2

## 7 Study Design and Methods

### 7.1 Study Overview

The study is a single center, Phase II randomised, double-blind crossover placebo-controlled trial in patients with localization-related epilepsy. Patients and examining physicians will be blinded to the treatment arm in which the patient is enrolled. Patients will use seizure calendars to record seizure frequency during baseline, active, and placebo phases. The study will last approximately 42-46 weeks (+/- 4 weeks). There will be up to 8 clinic visits. Patients may be inpatients for some study visits.

## 7.2 Recruitment

Subjects will be recruited from referrals to the NINDS Clinical Epilepsy Section (CES). Self-referral is permitted. We may make presentations at meetings of the Epilepsy Foundation and other non-profit venues to inform the public of the study. Patients and families who express interest will be given the approved NIH protocol description and appropriate contact information. We will advertise on IRB approved patient focused and research focused websites.

## 7.3 Screening

Patients will be screened in the Clinical Epilepsy Section (CES) outpatient clinic for inclusion in the protocol by CES physicians or licensed and credentialed practitioners under protocol 01-N-0139. MRI will be done under the screening protocol 01-N-0139. If inpatient video-EEG monitoring is needed to confirm seizure type, it will be performed under 01-N-0139 as well. That screening will include the following procedures which are standard care for intractable epilepsy:

Physical examination, vital signs, ECG

Clinical laboratory studies including standard clinical chemistry and hematology studies, urinalysis  
Pregnancy test for females of child-bearing potential

Review of epilepsy and general medical history

MRI scan if an adequate scan has not been performed before

Video-EEG monitoring if not performed previously

Measurement of plasma AED levels, if assay available

## 7.4 Study design

Following screening and a baseline phase (up to 6 weeks), patients will enter a treatment phase of 2 periods (Period 1 and Period 2) with a washout phase between periods 1 and 2. If patients have 4 seizures in less than six weeks during the baseline phase, they do not need to wait the entire 6-weeks to begin the treatment phase (Period 1) of the study. Each treatment period will last approximately 12-16 weeks. Following Period 1, there will be a wash-out of 4 – 6 weeks where no study medication will be taken. During each treatment period, there will be two Clinical Center visits. The first visit will entail clinical assessments and will occur 6-week +/- 2 weeks after starting the study drug and the second visit will entail clinical assessments and neuropsychological and mood assessment and will occur at the end of each maximum tolerated dose (MTD) treatment period. In addition, a follow-up visit will occur approximately one month following the end of the second treatment period that will include a physical examination and review of any adverse events. The total duration of the study is 42-46 weeks (+/- 4 weeks). Each clinic visit will last approximately one hour. The neuropsychological and mood evaluation at the end of each treatment period will last up to three hours.

## 7.5 Study procedures:

All specific study procedures are research-related. The PET scans and study drug administration are performed under INDs.

### 7.51 Baseline:

Baseline phase may occur concurrent with screening procedures and may last up to 6 weeks. During baseline, patients will record seizures on a seizure calendar, while on their baseline treatment with one or two AEDs. They will be eligible for this study if they have at least four seizures during a 6-week baseline phase. If patients have 4 seizures in less than six weeks, they do not need to wait the entire 6-weeks to begin Period 1 of the treatment phase. No changes in

patients' baseline AEDs will be allowed during this period, or subsequent study phases. Patients who use sublingual lorazepam for seizure clusters may continue to do so.

During the Baseline phase the following tests (described in section 7.57 and 7.58) will be performed (unless previously completed, as noted):

Columbia Suicide Severity Rating Scale

Neuropsychological testing

Mood testing

Measurement of plasma AED levels, if assay available

Pregnancy test

EEG

18F-FCWAY PET to measure 5HT1A receptor binding (if not already performed)

Saliva samples to test for polymorphisms in SERT, TPNH, COMT, BDNF and GABA genes that have been associated with psychiatric disorders and epileptogenesis (if not previously performed)

Blood samples for cortisol and ACTH level will be obtained at the time of PET (if performed).

#### 7.52 Randomization to Active drug or Placebo

Subjects will be randomized at the end of baseline to either active drug or placebo using a 1:1 ratio per the randomization schedule. The randomization schedule will be generated, secured, distributed, and stored by the NIH Pharmacy. Patients may be outpatients or inpatients during titration depending on their geographical location, need for additional education on the titration process or if they are participating in concurrent studies with the Clinical Epilepsy Section. All patients will be given an exact written titration schedule to follow.

#### 7.53 Period 1:

During Period 1 there will be regular communication with patients/families by phone, secure email, and/or the clinical trial database. Communication with patients/families will occur approximately 6 times during each treatment period, about once every two weeks.

PRX-00023 or matching placebo will be titrated up starting at an oral dose of 40 milligrams (Mg) twice daily for five days; the dose will then be increased to 80 milligrams twice daily for five days, and then to 120 milligrams twice daily for approximately 70 days. After which the dose will be tapered off as follows: 80 milligrams twice daily for five days, 40 milligrams twice daily for five days, followed by discontinuation of study drug. If patients experience side effects during the titration up, the next scheduled dose increase will be delayed until they abate. If this does not occur, the dose will be reduced in 40mg per day increments. Period 1 will last approximately 12-16 weeks. The above description and table below provides a targeted dosing schedule, however, adjustments may be made if, for example, the patient experiences side effects during titration.

	Titration		MTD	Taper	
Day	Day 0-4	Day 5-9	Day 10-79	Day 80-84	Day 85-90
No. of days	5 days	5 days	70 days	5 days	5 days
Dose	40mg bid	80mg bid	120mg bid	80mg bid	40 mg bid

Patients will keep seizure calendars. Patients will return to NIH 6 weeks +/- 2 weeks after the start of Period 1 and the tests listed in section 7.571 will be performed. At the end of the Maximum Tolerated Dose (MTD) period, patients will again return to NIH for repeat of baseline testing (see section 7.572). Following testing, patients will be tapered off of Period 1 study drug and begin washout period.

#### 7.54 Washout Period

Following the completion of Period 1, there will be a washout period for approximately 4 to 6 weeks.

#### 7.55 Period 2

Following a washout period, patients will be crossed over to the alternative treatment arm, using the same titration schedule as for Period 1. Patients may be outpatients or inpatients during titration. Outpatients will be given an exact written titration schedule to follow. During Period 2, there will be regular communication with patients/families by phone, secure email and/or the clinical trial database. Communication with patients/families will occur approximately 6 times during treatment Period 2; about once every two weeks. Patients will keep seizure calendars. Patients will return to NIH 6 weeks +/- 2 weeks after the start of Period 2 and the tests listed in section 7.571 will be performed. At the end of the Maximum Tolerated Dose period, patients will again return to NIH for repeat of baseline testing (see section 7.572). Following testing, patients will be tapered off of Period 2 study drug..

The same titration, MTD treatment, and taper schedule as described in Period 1 will be used for Period 2. Period 2 will last approximately 12-16 weeks..

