Objective: To initiate a pilot clinical trial assessing the safety, tolerability and efficacy of the 5HT1A receptor agonist PRX-00023 in patients with localization-related epilepsy. PRX-00023 is a 5HT1A receptor agonist that has shown promise in clinical trials of depression (Rickels et al 2008). Patients with localization-related epilepsy have reduced 5HT1A receptor binding on 18FCWAY positron emission tomography (PET). (Toczek et al 2003) Increasing neurotransmitter activity at 5HT1A receptor sites might ameliorate seizures. Moreover, depression is a common co-morbidity in people with epilepsy (Theodore et al 2006). Altered 5HT1A receptor binding has been found in depression.

Study Population: Thirty adults with localization-related epilepsy.

Design: A randomised, double blind, placebo-controlled cross-over, phase II clinical trial. Subjects will be screened under protocol 01-N-0139 and will undergo medical and epilepsy history and physical examination, vital signs, ECG, clinical laboratory studies including standard clinical chemistry and hematology studies, urinalysis, pregnancy test for females of childbearing potential, and MRI scan and video EEG monitoring will be performed if not previously completed successfully, and measurement of plasma AED levels (for those AEDs in which an assay is available at NIH).

The trial will have a baseline phase, which will last up to 6 weeks. Baseline may occur concurrent with screening procedures. The baseline phase will include measurement of seizure frequency (patient will record via seizure calendar). In addition the following will be administered, unless previously completed: Columbia Suicide Severity Rating Scale, neuropsychological and mood evaluations, FCWAY PET (if not already performed), EEG, measurement of plasma AED levels (if assay available), and pregnancy test (for women of child bearing potential), saliva samples will be obtained for genetic testing (if not previously obtained) and blood samples will be obtained during the PET procedure for cortisol and ACTH levels.

Following baseline, patients will begin the treatment phase (consisting of Period 1 and Period 2). Patients will be randomized to PRX-00023 (120mg BID) or matching placebo. After completion of the first treatment period, patients will undergo a washout period after which patients will be crossed over to the alternate treatment period.

Outcome measures:

1. Seizure frequency counts during the 3 month placebo and active treatment phases

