##### Physical Exam

Blood drawing for: CBC, acute care panel, hepatic panel  
Measurement of plasma AED levels, if assay available  
Urine Pregnancy test (for women of child bearing potential)  
Seizure calendar review  
Adverse event and toxicity record review  
Hamilton depression rating scale

7.572 At the end of each MTD treatment Period the following evaluations will be completed:

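### The protocol text lists no pregnancy test between the end of full dosing in Period 1 and the six-week visit of Period 2, so on the target schedule the last listed test is about 38-52 days old at the first Period 2 dose

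*Combined protocol and SAP*

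**What the plan says.** **Crossover.** Section 7.55 states: "Following a washout period, patients will be crossed over to the alternative treatment arm, using the same titration schedule as for Period 1". It names no test and no visit before the first Period 2 dose, and it lets titration be done as an outpatient on a written schedule. Section 7.54 says that after Period 1 "there will be a washout period for approximately 4 to 6 weeks", and section 7.4 makes that interval free of study drug.

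**Tests during treatment.** Section 7.57 gives test lists for two kinds of visit in each period: 6 weeks +/- 2 weeks after the start (7.571) and the end of the MTD phase (7.572). Both include "Urine Pregnancy test (for women of child bearing potential". Section 7.53 puts the end-of-MTD testing before the taper.

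**Before Period 1.** Section 7.3 lists "Pregnancy test for females of child-bearing potential" at screening. Section 7.51 lists a further pregnancy test in baseline without fixing a day, and says "Baseline phase may occur concurrent with screening procedures and may last up to 6 weeks". Section 7.52 attaches no test to randomisation: "Subjects will be randomized at the end of baseline to either active drug or placebo using a 1:1 ratio per the randomization schedule". The precis introduces its own list of baseline procedures with "In addition the following will be administered, unless previously completed", and that list contains "and pregnancy test (for women of child bearing potential".

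**Pregnancy rules.** Section 6.3 excludes pregnant women, and section 12.4 gives unknown teratogenic potential as the reason. Section 8.1 requires contraception during the study and for three months afterwards. A woman who becomes pregnant is dropped and unblinded.

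**The concern.** An exclusion for pregnancy protects a patient at dosing only if a reasonably recent test stands behind it. At crossover the listed schedule has a long gap. A conception during taper or washout would not be picked up by any listed test until well into Period 2. For women allocated placebo first, the start of Period 2 is the first exposure to PRX-00023. Because patients and examining physicians are blinded, a check cannot be confined to those about to start active drug, so it has to apply to every woman of child-bearing potential at crossover.

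What is at stake is fetal exposure. The primary endpoint, the power calculation and the significance level are not affected.

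**Working it through.** The plan states no interval from pregnancy test to first dose, so there is no figure of its own to reproduce. The check is calendar arithmetic on the target schedule.

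**Inputs**
- Dosing table, section 7.53: 5 + 5 days of titration, 70 days at 120 mg bid, 5 + 5 days of taper. The sum is 90 days, or 90/7 = 12.9 weeks, which fits the stated 12-16 weeks per period.
- Washout, sections 7.4 and 7.54: 4-6 weeks = 28-42 days.
- Mid-period visit, section 7.571: 6 +/- 2 weeks = 28-56 days after the start of the period.
- Baseline, section 7.51: up to 6 x 7 = 42 days.

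**Period 2**
1. Age of the last listed test at the first dose = taper + washout: 10 + 28 = 38 days to 10 + 42 = 52 days.
2. Sensitivity: the last taper label, Day 85-90, spans six days although the table says five. Counting six gives 39-53 days. Counting the washout from the start of the taper would give 28-42 days, but section 7.4 makes the washout drug-free, so that reading does not fit.
3. Time from first dose to the next listed test: 28-56 days. Of these, 10 are titration, so 28 - 10 = 18 to 56 - 10 = 46 days are at 120 mg bid.
4. Interval between consecutive listed tests: 38 + 28 = 66 days to 52 + 56 = 108 days.

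**Period 1**

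The baseline test is 0-42 days old at the first dose. The upper end needs a test on the first day and a full six-week baseline.

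**What a test at the end of washout gains**

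A urine test misses very recent conceptions. Call that blind spot L days; it applies to the old test as well as the new one. Without the new test, the window of undetected conception is (38 to 52) + L days. With it, the window is L days. The difference is the full 38-52 days, whatever L is.

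**Is an unlisted visit implied?**

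In the blood table of section 7.584, each period column is three times screening: 30/10, 9/3, 24/8, 48/16 and 87/29 all equal 3. Section 7.4 names only two visits per period. Three visits x 2 periods + baseline + follow-up = 8, which matches the ceiling of eight visits in section 7.1.

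**The case against.** The strongest objection is that the document most likely to fix test dates has not been seen. Section 26 lists a Study Calendar and an Eligibility checklist, and neither is in the text reviewed. The threefold blood volumes and the eight-visit ceiling suggest that a visit at the start of each period may be planned. Section 7.73 (Source of materials) has the pharmacy dispense three months' supply, which fits dispensing once per period, and some patients may be inpatients during titration. All of this stands as a reason for caution. It does not show that a test is planned: the period columns in section 7.584 are headed only with the six-week and 12-16-week points, and the narrative lists no test at crossover. A reader might infer that the trial has no pregnancy check before Period 2; the documents support only that the protocol text lists none.

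A reader might also infer that Period 1 is equally exposed. It is not. Women are tested at screening and again in baseline, and 42 days is a worst case because patients may start as soon as they have had four seizures. The precis wording might suggest that an old test can stand in without limit. Section 7.51, however, marks which procedures may be skipped if already done, and the pregnancy test is not so marked.

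Finally, contraception is mandatory and staff contact patients about every two weeks, so a recognised pregnancy could be reported. That lowers the risk but involves no test.

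**Conclusion.** The point holds for Period 2, as a minor safety improvement. On the protocol text and target schedule, the last listed pregnancy test is about 38-52 days old at the first Period 2 dose, and the next comes 28-56 days after it. This rests on testing before a 10-day taper, a drug-free washout of 4-6 weeks, and no further test in the Study Calendar.

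The Period 1 matter is secondary: the required test exists and needs only to be timed.

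A reader might infer that a material number of pregnancies would be exposed. The documents do not support this. They give neither the number of women of child-bearing potential nor a contraceptive failure rate, so no expected count is offered. With at most 30 patients and mandatory contraception, the number is probably very small. The case for acting is that the consequence could be serious and the remedy is trivial.

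**What to change.** **Main change.** First check whether the Study Calendar already has a test before the first Period 2 dose. In section 7.55, and in the Study Calendar if absent there, add: *Women of child-bearing potential must have a negative urine pregnancy test at the end of washout, before Period 2 study drug is released or started. A home or local test reported at an existing contact is acceptable. If the test is positive, study drug is not started and the pregnancy rule in section 8.1 applies.*

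**Secondary change.** In section 7.51, state that the baseline pregnancy test is done at randomisation.

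**Cost.** One urine kit per woman of child-bearing potential at crossover, so at most 30 even if every accrued patient were such a woman. No new clinic visit is needed. Timing the baseline test adds no kit. A woman who tests positive at crossover has no Period 2 data and drops out of the paired comparison, but under section 11.42 she can stay in the intent-to-treat population on Period 1 data. Section 8.1 would remove her at the six-week test in any case, so little is lost.

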#### 7.56 End of study

Patients will have a final follow-up visit approximately one month after the last dose of study drug. During this visit patients will have a physical examination and review any adverse events, ECG, blood and urine testing, and mood tests.

#### 7.57 Tests during the study

7.571 During the 6 week +/- 2 week visit the following evaluations will be completed:

##### Physical Exam

Blood drawing for: CBC, acute care panel, hepatic panel  
Measurement of plasma AED levels, if assay available  
Urine Pregnancy test (for women of child bearing potential)  
Seizure calendar review  
Adverse event and toxicity record review  
Hamilton depression rating scale

7.572 At the end of each MTD treatment Period the following evaluations will be completed:

##### Physical Exam

ECG  
EEG  
Blood drawing for: CBC, acute care panel, hepatic panel  
Measurement of plasma AED levels, if assay available  
Urine Pregnancy test (for women of child bearing potential)  
Neuropsychological tests and mood rating scales (see section 7.581)  
Columbia Suicide Severity Rating Scale

